2.5.3 Handling of missing values/censoring/discontinuations

The PDUS score and its components will be analyzed using a MMRM, which is valid under the MAR assumption. For analyses of these parameters, if all post-baseline values are missing then these missing values will not be imputed and the patient will be removed from the analysis of the corresponding variable, i.e. it may be that the number of patients providing data to an analysis is smaller than the number of patients in the FAS.

Data collected during the open label period (after Week 12) will generally be presented as 'observed case'; i.e. all available data for each time point will be included in the analyses.

2.5.4 Supportive analyses

Sensitivity analyses and supportive analyses will be conducted in order to provide evidence that the results seen from the primary analysis are robust. These analyses will center on the deviations in model assumptions, the treatment of missing data and protocol deviations/audit findings.

[REDACTED]

[REDACTED]

[REDACTED]

[REDACTED]

[REDACTED]

[REDACTED]

[REDACTED]

[REDACTED]

[REDACTED]

The GLOESS score will be revised to account for a small number of composite PDUS scores that are not in agreement with the definition of synovitis that power doppler alone does not mean synovitis ([D'Agostino \(2016\)](#), [Terslev L \(2016\)](#)). This endpoint will be named 'GLOESS revised (Definition 2).' and the primary analysis (MMRM) will be repeated on the revised definition.

2.6 Analysis of the key secondary objective

2.6.1 Key secondary endpoint

The key secondary efficacy variables are as follows:

- Proportion of patients with ACR 20 response at Week 12 in each treatment arm.
- Proportion of patients with ACR 50 response at Week 12 in each treatment arm.
- Change in SPARCC enthesitis index from Baseline to Week 12 in each treatment arm.

2.6.1.1 American College of Rheumatology response

The ACR response (reference Appendix 5.9 for details) will be used to determine efficacy ([Felson 1995](#)). A patient is defined as e.g. an ACR 20 responder if, and only if, the following 3 conditions hold:

- Patient has a $\geq 20\%$ improvement in the number of tender joints (based on 78 joints).
- Patient has a $\geq 20\%$ improvement in the number of swollen joints (based on 76 joints).
- Patient has a $\geq 20\%$ improvement in 3 of the following 5 domains:
 1. Patient's global assessment of disease activity (measured on a VAS scale, 0-100).
 2. Physician's global assessment of disease activity (measured on a VAS scale, 0-100).
 3. Patient's assessment of PsA pain (measured on a VAS scale, 0-100).
 4. Health Assessment Questionnaire-Disability Index (HAQ-DI[®]) score.
 5. Acute phase reactant (high-sensitivity C-reactive protein (hsCRP)).

An ACR 50 response is defined as a 50% improvement in at least 3 of the 5 measures and a 50% improvement in the SJC and TJC.

An ACR 70 response is defined as a 70% improvement in at least 3 of the 5 measures and a 70% improvement in the SJC and TJC.

2.6.1.2 Spondyloarthritis research consortium of Canada – enthesitis index

The SPARCC ([Maksymowych et al 2009](#)) enthesitis index focuses on the clinical evaluation and validation of the 16 sites shown in Table 1.

Table 1: Entheses sites comprising the total spondyloarthritis research consortium of Canada enthesitis index

Greater trochanter	R/L
Quadriceps tendon insertion into the patella	R/L
Patellar ligament insertion into the patella and tibial tuberosity	R/L
Achilles tendon insertion	R/L
Plantar fascia insertion	R/L
Medial epicondyles	R/L
Lateral epicondyles	R/L

Abbreviations: R = right, L = left

Tenderness at each site is quantified on a dichotomous basis: 0= non-tender and 1= tender. The sum of scores from each site is calculated to give a range of a total score for the index from 0 to 16.

2.6.2 Statistical hypothesis, model, and method of analysis

The following null hypotheses will be included in the testing strategy and type-I-errors will be set such that a family-wise type-I-error of 5% is kept:

Primary objective:

- H_1 : secukinumab s.c. is not different to placebo regimen with respect to the change in GLOESS from Baseline to Week 12.

[figure not shown]
See section 2.5.2 for details.

Key secondary objectives:

- H_2 : secukinumab is not different to placebo regimen with respect to ACR 20 response at Week 12.
- H_3 : secukinumab s.c. is not different to placebo regimen with respect to ACR 50 response at Week 12.
- H_4 : secukinumab s.c. is not different to placebo regimen with respect to the change in SPARCC enthesitis index from Baseline to Week 12.

No hypotheses other than H_1 to H_4 will be considered. The family wise error will be set to $\alpha=5\%$ (1-sided). The graphical approach of Bretz ([Bretz et al 2009](#)) for sequentially rejective testing procedures is used to illustrate the hierarchical testing strategy ([Figure 1](#)).

Figure 1 Testing strategy

The family-wise error will be set to $\alpha = 5\%$ (1-sided). H_1 is tested at α (1-sided). The following hypotheses will be tested sequentially and are included in the hierarchical testing strategy and type-I-errors will be set such that a family-wise type-I-error of 5% is kept:

The testing sequence will continue to H_2 at α (1-sided) only if H_1 has been rejected.

Similarly, the testing sequence will continue to H_3 at α (1-sided) only if H_2 has been rejected. This process will continue as each hypothesis is rejected up to H_4 .

Of note, in the description above, rejection of a hypothesis refers to rejection of the 1-sided hypothesis; however, the level of a rejected hypothesis is only passed on

(according to the graphical procedure) for the test of another hypothesis if the treatment effect is in favor of secukinumab.

ACR 20 at Week 12

Response at Week 12 in ACR 20 in the FAS will be evaluated using a logistic regression model with study treatment as a factor and baseline weight as a covariate. The odds ratios will be computed for comparison of secukinumab versus placebo using the logistic regression model fitted. In cases where separation is a concern for secondary endpoint at Week 12 an exact logistic regression model will be applied to all visits. To ensure convergence, this model will not include any continuous covariates. When exact logistic regression is unable to be implemented then Fisher's exact test will be applied. In this case no odds ratios or confidence intervals can be estimated but p-values may be calculated.

ACR 50 at Week 12

Response at Week 12 in ACR 50 in the FAS will be evaluated using a logistic regression model with study treatment as a factor and baseline weight as a covariate. The odds ratios will be computed for comparison of secukinumab versus placebo using the logistic regression model fitted. In cases where separation is a concern for secondary endpoint at Week 12 an exact logistic regression model will be applied to all visits. To ensure convergence, this model will not include any continuous covariates. When exact logistic regression is unable to be implemented then Fisher's exact test will be applied. In this case no odds ratios or confidence intervals can be estimated but p-values may be calculated.

Changes in SPARCC at Week 12

Between-treatment differences in the change from baseline in SPARCC at Week 12 in the FAS will be compared by means of a MMRM with treatment regimen and analysis visit as factors and baseline weight and SPARCC score as continuous covariates. Study treatment by analysis visit will be included as an interaction term in the model. An unstructured covariance structure will be assumed for this model. The significance of the treatment effect for secukinumab at different analysis visits will be determined from the comparison to placebo.

2.6.3 Handling of missing values/discontinuations

Missing data for the ACR 20 response and other binary efficacy variables (e.g. ACR 50, ACR 70, [REDACTED] PASI 75, PASI 90, PASI 100) for data up to 12 weeks (Week 12) will be handled as follows:

- Patients who drop out of the trial for any reason will be considered non-responders from the time they drop out through to Week 12.
- Patients who do not have the required data to compute ACR response (i.e. TJC and SJC and at least 3 of the 5 ACR core set variables) at the specific post-baseline time points will be classified as clinical non-responders.

The following continuous variables: ACR components, HAQ-DI[®] score, PDUS score and its components will be analyzed using a MMRM, which is valid under the MAR assumption. For analyses of these parameters, if all post-baseline values are missing then these missing values will not be imputed and the patient will be removed from the analysis of the corresponding variable, i.e. it may be that the number of patients providing data to an analysis is smaller than the number of patients in the FAS.

Data collected during the open label period (after Week 12) will generally be presented as 'observed case'; i.e. all available data for each time point will be included in the analyses.

2.6.4 Supportive analyses

Non responder imputation will be extended through to week 52 for ACR20, ACR 50, and ACR 70.

2.7 Analysis of secondary efficacy objective(s)

2.7.1 Secondary endpoints

The following secondary efficacy variables will be analyzed using the FAS population:

- Change in GLOESS from Baseline to Week 8.
- Change in OMERACT enthesitis score from Baseline to Week 12 for each of the 5 targeted entheses.

2.7.2 Statistical hypothesis, model, and method of analysis

The between treatment differences will be compared by means of a MMRM with treatment regimen, center, machine type and analysis visit as factors and baseline weight and baseline score as continuous covariates. Study treatment by analysis visit will be included as an interaction term in the model. An unstructured covariance structure will be assumed for this model. The significance of the treatment effect for secukinumab at different analysis visits will be determined from the comparison to placebo.

The OMERACT enthesitis score will be analyzed separately for each of the targeted entheses for both definitions of enthesitis score at a site level (see section 5.11).

2.7.3 Handling of missing values/censoring/discontinuations

Missing data will not be imputed for the secondary efficacy endpoints.

2.8 Other efficacy variables/Exploratory analysis

The following exploratory efficacy variables will be analyzed on the FAS for all applicable analysis visits unless otherwise specified.

- The response of ACR 20, ACR 50, ACR 70, PASI 75, PASI 90, PASI 100, [REDACTED]
- Change from Baseline in ACR components to week 12 [REDACTED]:
 - Changes in TJC 78 over time.
 - Change in SJC 76 over time.
 - Change in patient's global assessment of disease activity.
 - Change in patient's assessment of PsA pain.
 - Change in Physician's global assessment of disease activity.
 - Change in HAQ-DI response over time.
 - Change in hsCRP.

- [REDACTED]
- [REDACTED]

All results from the exploratory efficacy analyses will be interpreted descriptively.

For the double blind period;

- Continuous variables outlined above will be analysed using MMRM analysis analogous to that outlined for the primary efficacy variable, reference section 2.5.2 above.
- Binary outcome variables will be analyzed using logistic regression analogous to that outlined for the binary key secondary efficacy variables, reference section 2.6.2 above.

[REDACTED]

The Risk Ratio (RR) of ACR response in Secukinumab group / risk of ACR response in Placebo group will be determined. [REDACTED]

[REDACTED]

[REDACTED]

[REDACTED]

Non responder imputation will be extended through to week 52 for PASI 75, PASI 90 and PASI 100.

A horizontal bar consisting of three distinct black rectangles. From left to right: a small black rectangle, a large black rectangle, and a white rectangle. The white rectangle is positioned at the far right end of the bar.

100% of the time, the *labeled* and *unlabeled* data are drawn from the same underlying distribution.

— 7 —

[REDACTED]

For more information, contact the Office of the Vice President for Research and Economic Development at [contact] or [contact].

[REDACTED]	[REDACTED]

[REDACTED]

[REDACTED]

[REDACTED]

[REDACTED]

[REDACTED]

[REDACTED]

[REDACTED]

[REDACTED]

2.9 Safety analyses

All safety analyses will be based on the safety set. Only those visits which were pre-planned in the protocol will be reported in tables and figures for safety variables. All summaries will be performed on actual treatment received showing AEs observed up to the end of each Treatment period and the entire treatment period.

2.9.1 Adverse events (AEs)

Only Treatment-emergent AEs (TEAEs) will be summarized. Treatment-emergent AEs (TEAEs) are those AEs that started after the first dose of study treatment or events present prior to the first dose of study treatment but increased in severity based on preferred term and on or before last dose + 84 days.

TEAEs will be assigned to the last treatment received at the time of onset/worsening of AE. For summaries beyond treatment period 1, patients who switched from Placebo to Secukinumab will appear in both the population of patients for Placebo and Secukinumab (150 mg + 300 mg) treatment groups. If an AE occurred on the last day of treatment period 1 and the patient did not enter treatment period 2 it will be included as a TEAE in the treatment period 1.

Adverse events will also be reported according to MedDRA. The MedDRA version used for reporting the study will be described in a footnote.

Adverse events will be summarized by presenting, for each treatment group, the number and percentage of patients having any AE, having an AE in each primary system organ class and having each individual AE (preferred term). Summaries will also be presented for AEs by severity and for study treatment related AEs. If a patient reported more than one AE with the same preferred term, the AE with the greatest severity will be presented. If a particular AE 'severity' is missing, this variable will be listed as missing and treated as missing in summaries. If a patient reported more than one AE within the same primary system organ class, the patient will be counted only once with the greatest severity at the system organ class level, where applicable. Serious AEs will also be summarized.

The incidence of AEs will be presented per 100 patient years of exposure for the most frequent AEs ($\geq 2\%$ in any group) and SAEs.

Separate summaries will be provided for SAEs, other significant AEs leading to discontinuation and AEs leading to dose adjustment (including study treatment discontinuation).

A graphical display of the crude rates within system organ classes will be presented. The placebo group will be displayed with a bar whereas dots will be used for secukinumab treatment groups.

Non-treatment emergent adverse events will be summarized as well. These adverse events occurred before the first dose of the study treatment. The crude incidence rate will be provided without treatment information.

Algorithms for date imputations will be provided in Appendix 5.1.2.

Exposure time-adjusted incidence rates including 95% CIs will be presented for the entire treatment period. A graphical display of the crude rates and exposure-adjusted incidence rates will be presented for all AEs and SAEs by SOC.

In addition, for the legal requirements of clinicaltrials.gov and EudraCT, 2 required tables on TEAEs which are not SAEs with an incidence greater than 2% and on treatment emergent AEs and SAEs suspected to be related to study treatment will be provided by primary SOC and PT on Safety set population.

If for the same patient, several consecutive AEs (irrespective of study treatment causality, seriousness and severity) occurred with the same primary SOC and PT:

- A single occurrence will be counted if there is ≤ 1 day gap between the end date of the preceding AE and the start date of the consecutive AE
- More than one occurrence will be counted if there is > 1 day gap between the end date of the preceding AE and the start date of the consecutive AE

For occurrence, the presence of at least one SAE/SAE suspected to be related to study treatment/non-SAE has to be checked in a block e.g., among AEs in a ≤ 1 day gap block, if at least one SAE is occurring, then one occurrence is calculated for that SAE.

The number of deaths resulting from SAEs suspected to be related to study treatment and SAEs irrespective of study treatment relationship will be provided by SOC and PT.

2.9.1.1 Adverse events of special interest / grouping of AEs

Adverse events of special interest (AESI) of the Safety Profiling Plan (SPP) and the Risk Management Plan will be identified through an extraction from the electronic Case Retrieval Strategy database. The extraction will be performed by selecting those records where the drug name is AIN457 and the indication is psoriasis, psoriatic arthritis and ankylosing spondylitis.

To this end, the following events will be considered as adverse events of special interest:

- Major adverse cardiovascular events (MACE): identified per Novartis MedDra Query (NMQ) “MACE (MI, Stroke, Cardiovascular death)”
- Inflammatory bowel disease: identified per NMQ narrow “Inflammatory bowel disease”
- Infections and infestations: identified per SOC “Infections and infestations”
 - Fungal infectious disorders : identified per HLGT
 - Staphylococcal infections : identified per HLGT

- Herpes viral infections : identified per HLGT
- Mycobacterial infectious disorders : identified per HLGT
- Central nervous system infections and inflammations : identified per HLGT
- Oesophageal candidiasis : identified per SMQ narrow
- Infections of skin structures : identified per NMQ1
- Infectious pneumonia : identified per NMQ1
- Opportunistic infections : identified per NMQ1
- Malignancy: identified per NMQ “Malignant or unspecified tumours (SMQ excluding BCC and SCC)” or per SMQ for “Malignant or unspecified tumours

(SMQ)", "Skin tumours malignant and unspecified" or "Non-melanoma skin cancer (BCC and SCC)

- Hypersensitivity: identified per SMQ narrow "Hypersensitivity"
- Neutropenia : identified per NMQ
- Suicidal ideation and behaviour : identified per Suicide/self-injury (SMQ)
- Interactions with live vaccines : identified per HLT "Vaccination related complications"
- Hepatitis B reactivation : identified per HLT "Hepatitis viral infections"

The crude rates for AESIs will be summarized. In addition, listings will be provided presenting which subjects experienced which risk.

Important note: For the evaluation of AESIs risks, primary and secondary system organ classes of the MedDRA dictionary will be considered.

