1.1 Study design

This is a 52-week, multicenter, international study consisting of a 1 to 4-week Screening period, a 12-week randomized, placebo-controlled double-blind treatment period (Period 1), a 12-week open-label treatment period (Period 2) and a 6-month open-label extension period (Period 3), and a 12-week follow-up period after treatment completion.

Screening period

Eligible patients will be enrolled and enter a 1 to 4- week Screening period prior to randomization.

Treatment period 1 – placebo-controlled double-blind (Baseline to Week 12)

At Baseline, patients whose eligibility is confirmed will be randomized in 1:1 ratio in a double-blinded fashion to one of 2 treatment groups as follows:

- **Group 1:** secukinumab (150 mg s.c. or 300 mg s.c. depending on severity of skin lesions)
- **Group 2:** placebo

At each study treatment visit, all patients will receive 2 s.c. injections using PFSs since secukinumab is available in 1.0 mL PFSs. Patients assigned to secukinumab 150 mg will receive 1 PFS of secukinumab 150 mg and 1 PFS of placebo; patients assigned to secukinumab 300 mg will receive 2 PFS of secukinumab 150 mg; and patients assigned to placebo will receive 2 PFSs of placebo.

Primary analysis

The Week 12 analysis will be performed after all patients complete the Week 12 visit (see Section 2.15). Only the data analysts will be unblinded to the Treatment Period 1 randomization data after the Week 12 database lock/analyses. Summary results will be shared internally and externally; however, individual unblinded patient data will not be disclosed externally. The Ultrasonography Investigator and the Clinical Investigator will remain blinded from each other until the final database lock.

Treatment Period 2 – open-label treatment period (Week 12 to Week 24)

From **Week 12**, secukinumab will be given open-label to all patients irrespective of their initial treatment (i.e. only 150 mg or 300 mg secukinumab will be dispensed as 1 or 2 PFSs, respectively).

In **Group 1**, patients will continue to receive the same active dose of secukinumab every 4 weeks until Week 24 (i.e. at Week 12, 16 and 20); patients will no longer receive the placebo PFS, which was administered to maintain blinding.

In **Group 2**, patients will commence open-label secukinumab every 4 weeks from Week 12 until Week 24 (i.e. at Week 12, 16 and 20), based on their clinical characteristics (BSA or severity of skin lesions) at Week 12.

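### Section 2.9.1.1 assigns only crude rates to AESI groupings, and over the entire treatment period these are not comparable between secukinumab and placebo

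*SAP*

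**What the plan says.** Section 2.9 requires safety summaries by actual treatment, "showing AEs observed up to the end of each Treatment period and the entire treatment period". Section 2.9.1 adds that, beyond Period 1, "patients who switched from Placebo to Secukinumab will appear in both the population of patients for Placebo and Secukinumab". An entire-period table therefore has a placebo column and a secukinumab column, with switchers in both.

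Three statements in section 2.9.1 bear on exposure:

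- "The incidence of AEs will be presented per 100 patient years of exposure for the most frequent AEs". The threshold is 2% in any group, and SAEs are included as well.
- "Exposure time-adjusted incidence rates including 95% CIs will be presented for the entire treatment period". The events covered are not named.
- "A graphical display of the crude rates and exposure-adjusted incidence rates will be presented for all AEs and SAEs by SOC".

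Section 2.9.1.1 then lists the AESIs and how each is identified. Most are built from a Novartis or standardised MedDRA query (NMQ, SMQ), an HLGT or an HLT. One is a whole SOC: "Infections and infestations: identified per SOC". For the analysis it states "The crude rates for AESIs will be summarized" and adds patient listings. It neither mentions exposure-adjusted rates nor refers back to those in 2.9.1.

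**The concern.** A crude rate is the percentage of patients with at least one event. Two such percentages can be compared only if patients in both columns are followed for similar lengths of time. That holds in Period 1, where both arms have the same planned 12 weeks. It fails over the entire treatment period: placebo time ends when open-label secukinumab starts at Week 12, while secukinumab time can run to Week 52 plus the 84-day window for treatment-emergent events.

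The AESIs are the named risks that readers will look at first. If their entire-period tables carry only crude percentages, longer follow-up on secukinumab looks like a drug effect, and a real difference cannot be told apart from it. For groupings defined by query, HLGT or HLT, a reader cannot recover the right rate from other tables. These groupings combine preferred terms, sometimes across SOCs, and patient counts by term cannot simply be added.

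**Working it through.** The SAP gives no risk-time ratio and no expected AESI rate, so it has no figure to reproduce here. The check has two steps.

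**Inputs from the SAP.** 82 patients per arm; everyone on secukinumab from Week 12; last planned dose at Week 52 (section 1.1). Placebo exposure of switchers ends at the first Period 2 injection, and exposure after the last Period 3 injection runs for 84 days, i.e. 12 weeks (section 2.4.1). Treatment-emergent events are counted to last dose + 84 days (section 2.9.1). As a consistency check, Week 52 + 12 weeks = Week 64, the last visit in Table 5-1.

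**Assumption.** The share completing the extension, *f*, is not given. It is varied, with the rest taken to stop at Week 24 after a last dose at Week 20.

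**Step 1: risk time per patient (weeks)**

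- Placebo: 12.
- Group 1 on secukinumab: *f* × (52 + 12) + (1 − *f*) × (20 + 12).
- Switchers on secukinumab: the same minus 12.
- Ratio: mean of the two secukinumab values divided by 12.

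| *f* | Group 1 | Switchers | Mean | Ratio to placebo |
|---|---|---|---|---|
| 100% | 64.0 | 52.0 | 58.0 | 4.83 |
| 70% | 54.4 | 42.4 | 48.4 | 4.03 |
| 50% | 48.0 | 36.0 | 42.0 | 3.50 |
| 0% | 32.0 | 20.0 | 26.0 | 2.17 |

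The ratio reaches 4 when (48 − 26)/(58 − 26) = 0.69, so about 69% must complete the extension. A 5% drop-out before Week 12, with full completion otherwise, lowers the ratio from 4.83 only to 4.60–4.74, depending on when those patients had their last dose.

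Total exposure with full completion is 82 × 84/365.25 = 18.9 patient-years on placebo and 82 × (448 + 364)/365.25 = 182.3 on secukinumab.

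**Step 2: crude percentages under equal hazards**

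With the same constant rate λ per patient-year in both groups, the crude risk is 1 − exp(−λt). The secukinumab column averages the two sequences. The rates are assumed. With full completion:

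| Rate per 100 patient-years | Placebo | Secukinumab | Crude ratio |
|---|---|---|---|
| 2 | 0.46% | 2.20% | 4.8 |
| 10 | 2.27% | 10.51% | 4.6 |
| 50 | 10.86% | 42.54% | 3.9 |

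For the first row, t is 84, 448 and 364 days: 1 − exp(−0.02 × 84/365.25) = 0.46%, and the mean of 2.42% and 1.97% is 2.20%.

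At the other extreme (*f* = 0, t = 224 and 140 days) the same rate gives the mean of 1.22% and 0.76%, i.e. 0.99%, against 0.46%: a crude ratio of 2.2. An exposure-adjusted rate ratio would be 1.0 in every case.

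**The case against.** The strongest reply is that section 2.9.1 already answers the point. Its sentence on exposure-adjusted rates with 95% CIs for the entire period carries no restriction by frequency, seriousness or term, and 2.9.1.1 is a subsection of 2.9.1. A reader might infer that AESIs are reported by crude rate only, with no exposure-adjusted figure anywhere. The SAP does not support that. The by-SOC display covers the infections AESI, the grouping where the absolute contrast would probably be largest. Any AESI preferred term that is serious or reaches 2% in a group gets a rate per 100 patient-years. The general sentence could also be read to include the rest.

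These points stand, but they do not close the gap. The general sentence names no events. Where 2.9.1 does name a scope, it is frequent AEs, SAEs and SOCs, never the AESI groupings. The subsection written for those groupings names crude rates alone, and a programmer following it would produce only that. Even for infections, 2.9.1.1 considers primary and secondary SOCs while 2.9.1 tabulates by primary SOC, so the two counts may differ.

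Three further objections are fair:

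- Section 2.9 also requires summaries by period, so an unconfounded Period 1 comparison is already planned.
- AESI rates are to be summarised, not tested. The columns will still be read side by side.
- A placebo patient who never enters Period 2 can carry more than 12 weeks: a last injection at Week 8 gives 8 + 12 = 20. The 5% drop-out calculation shows the effect is small.

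**Conclusion.** The point holds as a gap in specification with a predictable direction of bias. For AESIs defined by NMQ, SMQ, HLGT or HLT, no exposure-adjusted summary is clearly assigned. Their crude entire-period percentages are not comparable between groups, because mean secukinumab risk time per patient is about 2 to 5 times that of placebo.

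The size depends on retention, which the SAP does not give. A reader might take 4- to 5-fold as fixed by the design. It is not: the extension is optional and Week 24 non-responders are withdrawn, so 4 or more needs about 69% to complete. The ratio stays above 2 in every scenario tabulated, so the bias shrinks with lower retention but does not vanish or reverse. The crude percentages quoted also assume equal, constant hazards at assumed rates. Period 1 crude rates and the SOC-level display for infections are outside the finding.

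**What to change.** In section 2.9.1.1, state that the exposure-adjusted incidence rates of 2.9.1, per 100 patient-years with 95% CIs, will be presented for every AESI grouping over the entire treatment period, whatever its frequency. State also that crude percentages serve for between-group comparison in Period 1 only, and put a footnote to that effect on the entire-period tables.

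The cost is a sentence or two in the SAP and another run of a table type already planned; section 2.4.1 already defines the exposure durations. The downside is wide intervals for rare AESIs. With 18.9 placebo patient-years and no events, the exact Poisson upper 95% limit is −ln(0.025)/18.9 = 3.69/18.9, or about 19.5 per 100 patient-years. That is the real uncertainty, which crude percentages would hide. Exposure adjustment also assumes a roughly constant hazard, and data after Week 12 are not a randomised comparison, so the Period 1 table should remain the main between-group evidence.
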